1. Gather formative data from focus groups of outdoor exercisers, both *Strava* users and non-users, on interest in receiving personalized, location-based sun protection advice and willingness to use sun protection advice sent through the *Strava* mobile app before and during physical activity.
2. Develop a machine learning algorithm to predict future time of day and duration of outdoor physical activity from activities logged on *Strava* through its API from users who consent to data access.
3. Modify the algorithms in *sunZapp* and social media messages from GSS to create a prototype of the SS intervention that delivers location-based, tailored sun safety advice to *Strava* users through *Strava* comments, which can be accessed through the *Strava* website and mobile app, and emails.
4. Test with *Strava* users the acceptability of the SS prototype and sun safety messages, ways of interacting

with it, and barriers/willingness to allowing access.

The R21 research is significant and innovative. A sun protection interface for the Strava platform will allow us to identify a large population of Americans at high risk for skin cancer who routinely engage in physical activity, often outdoors with high-risk sun exposure, and reach them with sun safety advice they may not seek on their own to motivate them to practice sun safety during outdoor activities. Dissemination of evidence-based sun safety messages through this widely-used “social network for athletes” is innovative. It will help to meet the goals set by both NCI and the U.S. Surgeon General to prevent skin cancer among physically-active Americans to reverse the one cancer currently increased by physical activity.

The project will be led by Principal Investigators, [name] and [name] at Klein Buendel, Inc. (KB). *Co-Investigators at Colorado State U., [name] (project statistician) and [name] (machine learning expert) will create the predictive algorithms, assisted by a machine learning graduate student.* [name], *project consultant*, at U. of Connecticut will provide expertise on physical activity promotion and interventions delivered via social media. [name], recent software engineer at *Strava, will also serve as a project consultant* and advise on delivering the sun protection intervention through *Strava*. Media developers at KB will produce the API database and program.

3A. SIGNIFICANCE

3A.1. The Skin Cancer Problem

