Using Facebook and investigators' networks, we will recruit a variety of exercisers, including those who use *Strava* for recreation only and for competitive training. Though not mutually exclusive, we will attempt to segment groups by these uses. *Strava* users (n=2 focus groups; n=16 total; 8 male, 8 female) will discuss a) *Strava* use, b) exercise behaviors, c) concerns about privacy, d) willingness to receive sun safety advice while exercising and e) use of sun protection while exercising. To explore interest in sun safety advice by those who track physical activity through other means, non-*Strava* users (n=2 focus groups; n=16 total; 8 male, 8 female; matched to Strava users in focus groups on race, gender, and activity type) will discuss exercise behavior, privacy concerns, and why they do not use *Strava*. Both groups will discuss time of day/day of week and season they exercise outdoors, activity type, sun safety intentions, tanning desirability, barriers to sun safety while physically active, SS concept, preferred sun safety content/delivery methods, barriers to using SS, utility/acceptability of sun safety advice through *Strava*, potential competitive advantages of sun safety, willingness to use the advice while exercising, and privacy concerns. We will not segment focus groups by age, but will examine age for differences in tailoring preferences. Transcripts will be coded and analyzed using ATLAS.ti.® *For this resubmission, we pilot-tested the focus group protocol (Box 1).*

3C.4. Development of Algorithms (Specific Aim 2)

[name], [name], and a computer science graduate student will develop a model that can predict impending outdoor physical activity by Strava users during high UV based on their uploaded activity records and relevant ambient factors (e.g., weather) and prescribe timely sun safety advice. We will use data-driven machine learning analytics to develop an algorithm that forecasts the next outdoor physical activity bout, assuming past behaviors and situational contexts predict future behavior.

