3C.4.1. Collect Retrospective Activity Data. Data from 1,000 tenured adult *Strava* users in the 4 U.S. Census regions will be obtained. *Eligibility criteria includes: 1+ full calendar year of activities; at least 156 activities [3 per week] in past year; 18 and older; U.S. resident.* Users will consent for their data to be accessed and a full calendar year of all *Strava* data will be procured, including following variables, *which are*

all available through the Strava API⁸⁰: distance, moving time, pace, elapsed time, start time, end time, date, type of activity (e.g., run; ride; *swim*), and gear used. These data will be paired with calendar data (i.e., day of week, season, holidays) and weather data *from National Oceanic and Atmospheric Administration databases* (i.e., temperature; precipitation; humidity; UV level; wind) to create a multivariate time series of data for each user. This data will be subjected to machine learning analytics to develop an algorithm that forecasts the likelihood that the user will engage in outdoor activity *in near future (duration of reliable prediction will be modeled)*, including the nature of exercise bout (e.g., length of time; UV level). We will recruit users by posting in clubs, a popular *Strava* feature (e.g., *Strava* Club has over 662,800 members⁸¹). We will post in various clubs until 1,000 eligible members are enrolled. Participants will receive an authentication screen (see **Figure 1**) that identifies data we will access and how it will be used. We will raffle off 10 \$50 gift cards as an incentive.

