3C.4.2. Use Machine Learning (AI) to Predict Outdoor Activity. Deep learning analytics, a branch of machine learning that mimics structures of the human brain, are innovative techniques that give more flexibility and are typically more accurate than autoregressive integrated moving average (ARIMA) models.^{82,83} To predict future outdoor activity, we will use a type of artificial neural network, Recurrent Neural Network (RNN), well-suited to temporal prediction,⁸⁴ along with a Long Short-Term Memory (LSTM) approach.⁸⁵ LSTM neural network can learn long-term patterns and dependencies and provide stability to prediction algorithm by evaluating when it is advantageous to remember or forget previous state, making assessing typically intractable problems with very complex data possible. LSTM has been applied to several temporal processing problems in public health, including influenza,⁸⁶ colorectal cancer,⁸⁷ and fall prevention.⁸⁸ We will build a machine learning model using Keras and TensorFlow in R. First, we will split time-series data into a training set and a validation set of users, in an 80/20 split. We will train a LSTM neural network on the training set. Once trained, we will layer on auxiliary calendar and weather data to try to reduce the model's error and maximize predictive power. We will compare models using several fit indices: Mean Absolute Percentage Error, Root Mean Squared Error, and Root Mean Squared Percentage Error, and plot predicted scores across each model with observed scores to determine closest match. We will apply the model with best fit and most accurate prediction to time-series in validation set to assess how well it predicts new data.

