3C.4.3. Integrate Predicted Outdoor Activity with Sun Protection Advice. Algorithms from our *sunZapp* mobile app⁷¹ (see **Box 2**) will be employed to tailor sun safety advice to predicted outdoor physical activity *and personal risk* of *Strava* users. *Machine learning model will predict users' risk of UV-exposure (i.e., timing and duration of outdoor exercise). Users' personal risk (i.e., skin type: hair and eye color and skin tanability⁸⁹) will be collected in SS user profile when first accepted by Strava users. We will use 5-day Planner in sunZapp to combine predicted time and duration of outdoor activity bout, forecast UV Index, and personal risk to calculate Strava users' time to sunburn and provide tailored sun safety advice, based on the World Health Organization's (WHO) Global UV Index guidelines.⁹⁰ To be modified based on results from focus groups.* we plan to deliver the advice in the evening and morning before the predicted outdoor physical activity bout (and during extended bouts) through *Strava* comments and emails (see **3C.5**). *Because Strava users get notified by email and in the app, they likely will see the message before their next outdoor activity.*

Box 2: Prior Research on Sun Safety Advice Algorithms

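### MAPE and RMSPE are unsuited to scoring whether an outdoor bout occurs, and Section 3C.4.2 does not say which series is scored or which index decides

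*Combined protocol and SAP*

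**What the plan says.** The target is described in several ways. Section 3C.4.1 wants an algorithm that "forecasts the likelihood that the user will engage in outdoor activity". Aim 2 in Section 2 is to "predict future time of day and duration of outdoor physical activity". Section 3C.4 sets out to "develop an algorithm that forecasts the next outdoor physical activity bout", and Section 3C.4.3 speaks of "timing and duration of outdoor exercise".

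Section 3C.4.2 gives the method. "First, we will split time-series data into a training set and a validation set of users, in an 80/20 split". An LSTM network is trained on the training users, and the team will then "layer on auxiliary calendar and weather data to try to reduce" its error. On selection it says: "We will compare models using several fit indices: Mean Absolute Percentage Error, Root Mean Squared Error, and Root Mean Squared Percentage Error", together with a plot of predicted against observed scores. Last comes validation: "We will apply the model with best fit and most accurate prediction to time-series in validation set".

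The section does not say which series or time step is scored, how periods without activity are handled, which index decides if the three disagree, or which measure is reported in the validation users. The Statistical Analysis Plan does not mention the algorithm. Section 3C.5 uses the predictions to decide who is sent a message and when, with advice triggered when the forecast UV Index is 3 or more during the predicted activity.

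**The concern.** A message is triggered by a forecast that a bout will take place, so the forecast can fail in two ways: a missed bout, or a message before a rest day. MAPE and RMSPE divide each error by the observed value. For an outcome coded 1 for activity and 0 for none, they have no finite value on the inactive periods. The usual workaround is to drop those periods, but that removes the second kind of failure from the score. A model that forecasts activity too readily then looks better than one that separates active days from rest days.

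At stake is which model goes into the prototype, and whether the study can report how often a message preceded a real bout. That figure would be useful in planning the later randomized trial.

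**Working it through.** **Inputs from the plan.** The activity floor is 156 a year (Section 3C.4.1), which agrees with 3 × 52 = 156. There are 1,000 users, and an 80/20 split gives 800 training and 200 validation users. Box 1 reports that 41% of surveyed Strava users upload at least 5 times a week, and 5 × 52 = 260 a year. The plan states no performance figure for the algorithm, so there is none to reproduce.

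**Formulas**, for observed y and forecast f:
- MAPE = mean(|y − f| / |y|)
- RMSPE = √mean(((y − f)/y)²)
- RMSE = √mean((y − f)²)

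**Share of periods with y = 0.**
- Daily grid, 156 activities: (365 − 156)/365 = 209/365 = 57.3%.
- Daily grid, 260 activities: (365 − 260)/365 = 28.8%.
- Both are lower bounds at those counts, because two activities can share a day and some may be indoors.
- Hourly grid within 10 AM to 4 PM (the high-UV window of Section 3A.3), every bout assumed to fall there and to touch 1 to 3 clock hours: 6 × 365 = 2,190 hours. At 156 bouts, 1 − 468/2,190 = 79% to 1 − 156/2,190 = 93%. At 260 bouts, 1 − 780/2,190 = 64% to 1 − 260/2,190 = 88%.
- Duration of bouts that occurred: 0%, so both percentage indices are defined there.

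**Effect of dropping the zero days** (daily grid, 156 active days). The user's habits are assumed: three habitual weekdays with probability 0.80 and four other days with probability 0.148.

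Flat forecast of 0.8 every day:
- MAPE = RMSPE = |1 − 0.8|/1 = 20%.
- RMSE over all days = √[(156 × 0.04 + 209 × 0.64)/365] = √(140/365) = 0.62.

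Calibrated weekday forecast (0.80 or 0.148):
- Habitual days: 365 × 3/7 = 156.4, of which 0.80 × 156.4 = 125.1 are active. The other 30.9 active days fall on non-habitual days.
- MAPE = (125.1 × 0.20 + 30.9 × 0.852)/156 = 33%.
- RMSPE = √[(125.1 × 0.04 + 30.9 × 0.726)/156] = 42%.
- RMSE over all days = √(3/7 × 0.80 × 0.20 + 4/7 × 0.148 × 0.852) = √0.1406 = 0.37.

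Both percentage indices prefer the flat forecast, and RMSE prefers the weekday forecast. At an assumed message cut-off of 0.5, the flat forecast would flag all 209 rest days. The weekday forecast would flag 0.20 × 156.4 = 31.

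**Relation to the Brier score.** For y in {0, 1} and a probability forecast, the mean of (y − f)² is the Brier score, so RMSE is its square root and ranks models identically.

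**Where the three indices agree.** Compare the weekday forecast with a flat forecast at the base rate, 156/365 = 0.427, for the same user. The base-rate forecast has MAPE and RMSPE of 57% and RMSE 0.495. The weekday forecast has 33%, 42% and 0.37. All three indices prefer the weekday forecast, so the distortion appears when a candidate over-forecasts and not in every comparison.

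**The case against.** Several points on the other side stand.

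- *A usable index is already named.* RMSE is defined at zero and is equivalent to the Brier score on a 0/1 series. A reader might infer that the plan has no quantitative measure of occurrence at all. The text does not support that. What is missing is a statement that RMSE is applied to that series and that it decides.
- *The percentage indices have a legitimate use.* They are defined for the duration of bouts that occurred, which is also a stated target.
- *The flat 0.8 forecast is not a candidate in the plan.* It shows what the indices reward, not what this study will select.
- *The plan's comparison without and with calendar data.* A reader might infer that it would pick the wrong model. On a daily expected-minutes series, a constant forecast and a weekday forecast can indeed be ranked in opposite orders. With 260 active days, mean bout 45 minutes and bout-length CV 0.5, RMSE is 27.8 against 24.4, MAPE 36% against 44% and RMSPE 46% against 59%. But those inputs are assumed, and no section names expected minutes as the scored series. The plan's base model is an LSTM, which may learn weekly habits before calendar data are added.
- *Selection data.* A reader might infer leakage into the validation users. None is shown. The order of steps implies comparison on the training users, and holding back 200 users is sound. The text describes no tuning set or cross-validation within the 800, but that does not establish that none will be used.
- *Other checks exist.* The plots could reveal bouts forecast on rest days. The usability interviews with 30 users (Section 3C.5.3) and the Month 15 review (Study Procedures) consider accuracy and validity, but they follow selection and name no metric. The held-out users test the chosen model; they cannot bring back a better one already rejected.
- *This is exploratory R21 work.* The forecast horizon is reasonably left open, but a scoring rule can still be fixed beforehand.

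**Conclusion.** The point holds for MAPE and RMSPE as indices for whether a bout occurs. If scored daily, they are undefined on at least 57% of days at 156 activities a year and 29% at 260. With those days dropped, they ignore false alerts and can favour an over-forecasting model (20% against 33% for MAPE in the illustration, where RMSE ranks the other way). The zero shares rest on an assumed time grid, and the ranking example on assumed habits. Neither shows that this study's data will produce a wrong choice.

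The gap is confined to Aim 2. The primary paired t-test and the sample size do not depend on it. It is a cheap improvement, not a threat to the pilot's main analysis.

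**What to change.** Amend Section 3C.4.2 as follows.

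- State the scored series and the time step, and do not use MAPE or RMSPE for occurrence.
- Score whether a bout occurs, per stated period with UV Index at or above 3 (the plan's own message trigger). Use Brier score (equivalently RMSE on the 0/1 series) or log loss, and name it in advance as the deciding index.
- Report precision and recall at the message cut-off.
- Score the start time and duration of bouts that occurred by MAE or RMSE in minutes.
- Compare candidates by user-level cross-validation within the 800 training users, then report the same measures once in the 200 held-out users.

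No new data are needed. The cost is some wording, a little more computing, and a cut-off fixed in advance. Reported accuracy may also look less favourable.

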2.7. Study Timeline

FIGURE 1: PROJECT TIMELINE

	1	2	3	4	5	6	7	8	9	10	11	12	13	14	15	16	17	18	19	20	21	22	23	24
Create and Review Study Protocols																								
Focus Groups with Outdoor Exercisers																								
Prediction Algorithm Creation																								
Database and Prototype Development																								
Usability Testing																								
Review of Results																								
Pilot Field Trial																								
Data Analysis																								

Protection of Human Subjects RISKS TO HUMAN SUBJECTS

Human Subjects Involvement, Characteristics, and Design. The subject population for this study is adults who engage in routine physical activity and log their activities on *Strava*, an activity tracking and social network site with accompanying mobile app. Both males and females will be included and participants will be of various ethnic and racial backgrounds. Potential participants will not be excluded based on ethnic group or race. Participants will be asked to complete consent and demographic forms. The demographics of the expected participants are detailed in the Targeted Enrollment Table. Human subjects will include:

1. **Focus Group Participants (n=32):** Adult *Strava* users and nonusers will provide feedback regarding concept of *Strava Sun* (SS), preferred content of sun safety advice and delivery methods, their outdoor activities and time of day/day of week they typically exercise outdoors, variation in outdoor exercise by season, confidence and barriers to using SS advice, utility/effectiveness of advice for sun protection through *Strava* community, willingness to use the advice while exercising, and concerns around privacy. Current *Strava* users (n=2 focus groups; n=16 total; 8 male, 8 female) will be convened in Denver for a discussion on a) *Strava* use, b) exercise behaviors, c) concerns about privacy, d) willingness to receive recommendations on preventing sunburn while exercising, and e) *use of sun protection while exercising*. A group of outdoor exercisers who do not use *Strava* will also be convened (n=2 focus groups; n=16 total; 8 male, 8 female; *matched to Strava users in focus groups on race, gender, and activity type*). Inclusion criteria are 1) being 18 years of age or older, 2) speaking and reading English, 3) consenting to participate, and 4) being a regular user of *Strava* (*Strava* users group only). Exclusion criteria includes 1) having a cognitive or visual impairment that would interfere with participating, 2) being unwilling to be audio/video recorded, and 3) having another family member participating in the research. Focus group transcripts will be coded and analyzed using ATLAS.ti® software. Participants will be compensated \$50 for their time.
2. ***Strava* Users in the USA to Provide Activity Data (n=1,000):** These participants will not answer survey questions or actively participate in the program. They will provide authentication to collect their retrospective (one year of data) activity data through the *Strava* API. We will not collect their current activity data. The data being collected and what it will be used for will be detailed in the authentication. These users will be recruited by posting in clubs on *Strava*, until 1,000 eligible users have agreed to provide their data. Eligibility requirements include: 1) having at least 156 activities uploaded in one year of *Strava* use; 2) providing authentication. They will be entered to win one of 10 \$50 gift cards for allowing access to their data.
3. **Usability Test Participants (n=30):** Usability testing of the intervention will be conducted with 30 *Strava* users who previously consented to provide their data for analysis and creation of the algorithm (see above). These participants will have already provided consent for data access, but will be re-contacted by email through the *Strava* API to ask if they are interested in participating in the usability testing. The first 30 *Strava* users to respond to the emails will be enrolled and will receive informed consent before starting a condensed intervention period. Identifying the 30 participants in the SS database, we will send out the created messages by email and comments for four weeks. At the completion of the four-week period, participants will complete a phone interview with project staff to assess recall of messages, message delivery and timing (*e.g., if message received before next physical activity bout*), accuracy of outdoor activity predictions, and usability of and problems with SS comments/emails. *They will be asked about sun protection practices during physical activity*. Eligibility requirements include: tenured *Strava* user (member for at least one year with 156 activities);

18 or older; United States resident; can read/write in English; and provides authentication for data collection. Participants will be compensated \$40 for their time.

4. **Pilot Field Testers (n=226):** *Strava* users (n=176) will test the prototype *SS* interface while interacting with the *Strava* platform and community in the United States. They will be recruited through posting an invitation in *Strava* clubs. The invitation will link them to the study website where they will receive more information and be screened and consented. Participants will provide feedback on the design, appeal, and functionality of the *SS* message delivery and complete measures of self-efficacy, response-efficacy, sun protection practices, *sunburn (defined as skin red and/or painful from exposure to the sun in the past four months)*, and barriers to sun protection, recall of *SS* messages (i.e., how many times a day they read the notifications, how much they liked receiving them, preferred type of message), and acceptability and willingness to use *SS* interface through *Strava* in the future. Additionally, a small control group (n=50) will be included to determine if a no-treatment control condition is acceptable to *Strava* users and estimate follow-up rates for planning a randomized trial. The control group sample is not designed to test for statistical differences in comparison to the treatment group. *Randomization should assure that the control group is similar in age, gender, and activity level.* Inclusion criteria are 1) being 18 years of age or older, 2) writing and reading English, 3) being a regular user of *Strava* (at least 3 uploads per week), 4) living in the United States, and 5) consenting to participate. Exclusion criteria includes 1) having a cognitive or visual impairment that would interfere with participating, 2) having another family member participating in the research, or 3) being unwilling to give consent. They will also be excluded if they participated in a focus group or usability testing. Participants will be compensated \$65 (\$30 at baseline and \$35 at follow-up) for their time. Control group participants will be compensated \$45 (\$20 pretest, \$25 posttest) for completing the surveys.

Study Procedures, Materials, and Potential Risks.

Study Procedures: The two-year R21 research will use scientifically-rigorous formative research and pilot-testing. Investigators will create study protocols in Month 1. Outdoor exercisers, including *Strava* users and non-users, will give input on initial concepts for *Strava Sun (SS)* in focus groups during Months 2-5. An algorithm that predicts time of day and day of week spent exercising outdoors will be developed using anonymous *Strava* user data in Months 6-8. A prototype of the *SS* database will be developed in Months 9-14 and the messages and delivery methods will be tested for usability and acceptability with *Strava* users. In Month 15, investigators and expert consultant will give input on the formative research results, validity of the time outside algorithm, usability of *SS*, and the pilot-test plans. In Months 16-21, the feasibility of *SS* will be tested in a pilot field trial with *Strava* users. Data analysis on the pilot field trial will be performed in Months 22-24. All procedures will be approved by the Western Institutional Review Board (WIRB), KB's IRB (IRB costs are paid from KB's indirect costs).

The collaborating site is Colorado State University (FWA No. 00000647).

Study Materials: Data from focus groups, usability testing, and pilot field test will be collected in the form of handwritten notes, video and audio tapes, computer files, transcriptions, online surveys, and web server records. We will collect retrospective (one year of data) activity data through the *Strava* API to develop the algorithm predicting outdoor physical activity. Data will be obtained specifically for research purposes and will be kept confidential with access limited to the Multiple Principal Investigators (MPIs), Co-Investigator, specific project staff, and consultants. Data will be obtained specifically for research purposes and will be kept confidential with access limited to the MPIs and specific project staff. All data will be kept in locked files.

Potential Risks: Potential risks to adult *Strava* users and non-users are minimal, mainly social or psychological. Participants may be hesitant or uncomfortable responding to questions about outdoor physical activity and actions to protect their skin from the sun. They also may not feel comfortable responding to questions about their opinions on appeal, ease of understanding, navigation, and functionality of the prototype *SS* and barriers and willingness to use it. Responses will not be shared with anyone except project staff. All participants will be allowed to withdraw at any time if they are uncomfortable with the discussions or survey questions. Responses to the questions will be coded to protect confidentiality, and participants may choose to not answer questions. WIRB requires that the option not to answer be provided to all participants on all questions.

ADEQUACY OF PROTECTION AGAINST RISKS

Informed Consent and Assent. Human Subjects oversight will be conducted by the Western Institutional Review Board (WIRB; DHHS IRB Reg. No. IRBooooo053; FWA No. 00003715), KB's IRB. All consenting procedures will be IRB-approved. The WIRB will review and approve subject materials (including

recruitment advertisements, letters, consent forms, survey instruments) and data management procedures prior to study implementation.

Focus group participants will be presented with IRB-approved consent forms that will describe the purpose of the project, risks and benefits, and selection criteria. Participants will be given an opportunity to ask questions and have them answered. For focus groups, consent will occur in-person and will be administered by investigators. For the usability test and for participants providing retrospective data, a link to an online informed consent document will be provided to participants. Participants will have the option to print the consent form. For the pilot field test, online consent will occur prior to the pretest survey and randomization. Again, there will be an option for participants to print the consent language.

Participation will be voluntary, with the right to stop participating at any time. No clinical data will be captured. Responses to survey questions and the discussions would not reasonably place the participants at risk of criminal or civil liability or be damaging to the participants' financial standing, employability, or reputation. All data coding, data entry, analysis and reporting activities will be conducted by KB and CSU. Participants will be informed that they have a right to withdraw from the study at any time. No additional data will be collected from participants who decide to withdraw; however, the information collected prior to withdrawal will remain in the study.

Protection Against Risk. To minimize potential psychological risk, the focus group facilitator ([name]) will establish ground rules for discussion that includes an open, non-evaluative exchange of comments and ideas. All surveys and data collection forms will be approved by WIRB and employed under the supervision of senior project staff. Participants will be told that they do not have to answer any questions which make them uncomfortable and can terminate their participation at any time they wish.

Notes, surveys, audiotapes, and data will be accessible only by research personnel. Responses to survey questions would not reasonably place the subjects at risk of criminal or civil liability or be damaging to the subjects' financial standing, employability, or reputation. No clinical data will be captured. The data collected on this project will be obtained with the "use of educational tests, survey questions, [and] interview procedures."

Data will be de-identified before being submitted for analysis. All notes and printed data collection forms and questionnaires will be stored in locked cabinets at KB offices; all electronic data files will be stored on KB's secure network servers behind computer firewalls, with routine backup. All identifiers will be stored in secure files and behind computer firewalls and results will be shared in aggregate form only. All human subjects participating in this project will be 18 years and older.

To minimize the risk to participant data privacy and protection through the internet, KB programmers will monitor and maintain all programs and databases and use an established protocol for participant cyber safety and security. KB is HIPAA complaint and maintains vigorous technical safeguards which are built into KB's IT system to protect information and to control access to it. All participant information will be protected using 128-bit SSL encryption. All Internet information must travel through KB's CISCO ASA 5505 firewall using ASA software version 9.0(2) encrypted 3DES-AES. Traffic then moves to KB's web server. This server is a Dell Power Edge T-310 with 32 GB of RAM, 1.5 TB available disk space on a RAID 5 redundant drive system using Windows Hyper-V Operating System. The virtual web server uses Windows 2008 IIS Web server software. User click stream data is collected using Webtrends and is saved to our SQL server. Enrollment data is transferred to our SQL server (Windows Server 2008) which uses MS SQL server 2008 R2 database software. This machine is also a Dell Power Edge T-310 with 32 GB of RAM, 1.5 TB available disk space on a RAID 5 redundant drive system using Windows Hyper-V OS and has no access to the Internet. When a participant is directed to take a survey, their computer is linked to a third server in our system which is also a Dell Power Edge T-310 with 32 GB of RAM, 1.5 TB available disk space on a RAID 5 redundant drive system using Windows Hyper-V OS. This server runs Question Pro Survey software. Data from each survey is collected and saved to the SQL server mentioned above. All network traffic is sent from the CISCO firewall to a Syslog server using Manage Engine Firewall Analyzer 7 software. Login and network activity is required and monitored by Windows servers to an event viewer. Servers are kept in a locked room on site. All files are secured locally using MS NTFS. All traffic between servers and PCs on the LAN are digitally signed communications. Each local machine has a built-in operating system firewall. Data from the Question Pro surveys are exported for data analysis by local machines which are also behind KB's firewall. Access to this exported data by outside sources is done using File Transfer Protocol (FTP) protected by Secure Socket Layer (SSL). SQL databases are protected by the built-in security of MS Active Directory. Data is backed up using a Quantum SuperLoader 3 tape library using LTO4 tapes that contain 800 GB/1.6 TB of info (depending on compression used). The device holds 16 tapes. The backup software used by KB is Symantec Back-up Exec. 2012. Daily backups are incremental and tapes are recycled weekly. Weekly backups are done every Friday and are recycled every 6 weeks. Monthly backups are done on the last Friday of each month and are full backups of all data. These monthly tapes are stored in a secure offsite facility and are never recycled.

With regards to app security on personal devices, Apple (e.g., iOS programmed apps) completes a full

security review of any app installed on a phone including beta/testing apps through their App Transport Security (ATS). KB App programming will include all key developer-related features to ensure ATS security. Google Play (Android programming) does not conduct a similar security check; however, KB has extensive experience with developing and marketing both iOS and Android programmed apps using an established protocol (SSL/TLS: Secure Sockets Layer/Transport Security Layer) and has never experienced a data breach. All usability testers will be informed that information being sent to and from their device will remain encrypted and password protected, and at any time they are allowed to opt-out of the program.

POTENTIAL BENEFITS OF THE PROPOSED RESEARCH TO PARTICIPANTS AND OTHERS

Potential benefits for all participants will be the knowledge that they have helped in development of an innovative mobile delivery system for preventing the development of skin cancer. Participants also may increase their knowledge of effective sun protection practices. A sun protection interface for the *Strava* platform will provide individuals who engage in regular physical activity advice to help them plan for and practice sun safety during outdoor activities.

A description of this study will be available on <http://www.ClinicalTrials.gov>, as required by U.S. Law. This website will not include information that can identify the participant. At most, the website will include a summary of the results. This website can be searched at any time.

IMPORTANCE OF THE KNOWLEDGE TO BE GAINED

Skin cancer is the most preventable cancer because excessive exposure to ultraviolet radiation (UV), the primary risk factor, is easily modifiable. Unfortunately, skin cancer rates continue to rise and many Americans experience sunburns. Physical activity is associated with increased prevalence of sunburn and melanoma. The proposed research is important because it will develop new mHealth strategies to reduce the epidemic of skin cancer in the United States. In addition, the app will provide Americans who engage in physical activity, a healthy lifestyle behavior, real-time advice on sun safety, when and where they need it.

TRAINING IN THE ETHICAL CONDUCT OF RESEARCH WITH HUMAN SUBJECTS

The MPIs, Co-Investigators, and study personnel have completed the required training in the Ethical Conduct of Research with Human Subjects. Necessary documentation will be provided to NIH prior to funds being awarded.

DATA AND SAFETY MONITORING PLAN

A data safety and monitoring plan will be implemented for this R21 project, following well-established procedures at KB. We will not set up an independent Data Safety and Monitoring Board because this study is low risk; does not include use of therapeutics; and physical risks are not anticipated. However, the progress of the formative research will be monitored monthly by the MPIs, Co-Investigators, and study staff who will meet weekly to discuss the activities in the project, participant recruitment, and data collection. Any critical events will be reviewed by the investigators to ensure that project methods have not been intrusive or disruptive. Annual reports on data safety and monitoring are submitted to WIRB. Compliance with data collection protocols will be monitored throughout data collection by the investigators. The investigators are responsible for reporting all adverse events to the IRB. Only Grade 1 events are expected on this trial. Thus, adverse events will be reported annually, as required by DHHS. This report will be reviewed by WIRB. Any action taken by the IRB or project investigators resulting in a temporary or permanent suspension of the trial will be communicated immediately by the contact PI to the NIH program officer.

Statistical Analysis Plan

Focus groups will be recorded, transcribed, and analyzed using Atlas-ti[©] software by assigning codes that categorize views, themes, and opinions, rely on constant comparative analysis and a phenomenological approach. In the pilot field trial, primary outcome is change in sun protection pre to post, analyzed with a paired t-test; changes in perceived risk, response- and self-efficacy, and sunburn will be compared pre to post, similarly. Message recall (i.e. receipt of the messages), users' reactions, barriers, and willingness to use SS, will be summarized as proportions/means and compared on demographics, using chi-square tests, t-tests, and correlations at $p=0.05$ (2-tailed). Power analysis was estimated using treatment effect sizes from our sunZapp trials. For this small-scale pilot test, we powered on the quasi-experimental pretest-posttest comparison within the SS group, using a paired samples t-test. Assuming an effect size of 0.23 in sun protection pre to post and a correlation between the pre/post scores of 0.5, we will need 181 participants with complete pre-post data to detect an effect of this size with power of 0.80 in a 2-tailed $p=0.05$ test, which we factored up to 226 to account for 20% attrition. Recruitment rates and duration, and follow-up rates, will be described for planning a future randomized trial on SS effectiveness. We will test if sun safety messages (SS message recall) reduced physical activity (IPAQ), using correlations. The control group sample is not designed to test for statistical differences in comparison to the treatment group. Data will be de-identified and stored in KB's secure servers. [name] will oversee data management and analysis. SAS will be used for analyses.
